#### **4.3.2. Sample Size Re-estimation**

Not Applicable.

#### **4.4. Randomization**

In this open-label study, eligible subjects will be randomized 1:1 to one of the two KRX-0502 starting dose groups with approximately 100 subjects per group:

- Group 1: KRX-0502 1 tablet TID (total of 3 tablets/day) with meals
- Group 2: KRX-0502 2 tablets BID (total of 4 tablets/day) with the largest 2 daily meals

#### **4.5. Clinical Assessments**

The complete schedule of assessments for this study is presented in Table 2 of the protocol.

Data from the central laboratory will be used for efficacy and safety analyses including analyses for supportive and exploratory endpoints. The following laboratory evaluations will be performed at the central laboratory:

- A complete blood count (CBC); including white blood cell (WBC), white blood cell types (WBC differential), red blood cell (RBC) count, hematocrit (HCT), Hgb, RBC indices and platelet (thrombocyte) count will be performed at Visit 1A (Screening) and, if applicable, Visit 1B (Re-screening); Visit 2 (Randomization); and all subsequent visits.

- A complete chemistry profile (CCP); including sodium, potassium, phosphorus, calcium, calcium adjusted for albumin, chloride, carbon dioxide/bicarbonate, glucose, blood urea nitrogen [BUN], creatinine, estimated glomerular filtration rate (eGFR) based on the Modification of Diet in Renal Disease (MDRD) Study equation, aspartate aminotransferase [AST], alanine aminotransferase [ALT], alkaline phosphatase [ALP], total bilirubin, total protein, and albumin) will be performed at Visit 1A (Screening) and, if applicable, Visit 1B (Re-screening); Visit 2 (Randomization); and all subsequent visits.
- Iron studies (TSAT, ferritin, transferrin, unsaturated iron-binding capacity [UIBC], total iron-binding capacity [TIBC] and serum iron) will be performed at Visit 1A (Screening) and Visit 1B (Re-screening), if applicable, Visit 2 (Randomization); and all subsequent visits.
- FGF23 (intact and C-terminal) testing will be performed at Visit 2 (Randomization), Visit 9 (Week 24), Visit 12 (Week 48), and the Early Termination (ET) visit.
- Intact parathyroid hormone (iPTH) testing will be performed at Visit 1A (Screening) and if applicable, Visit 1B (Re-screening); Visit 2 (Randomization); Visit 9 (Week 24); Visit 12 (Week 48); and the ET visit.

The laboratory parameters used in the assessment of efficacy are:

- Hgb,
- TSAT,
- Ferritin and
- Serum phosphate

The schedule for the additional efficacy assessments is as follows:

- Work Productivity and Activity Impairment (WPAI) Questionnaire and FACIT Fatigue Scale Questionnaire will be administered at Visit 2 (Randomization); Visit 9 (Week 24); Visit 12 (Week 48); and the ET visit.
- Number of hospitalizations and duration (days) will be assessed at each visit.

In addition to the laboratory assessments listed above, the safety assessments schedule includes the following:

- AEs will be collected starting at the time of informed consent.
- Vital signs (seated heart rate and blood pressure after at least 5 minutes of rest) will be recorded at Visit 1A (Screening) and, if applicable Visit 1B (Re-screening); Visit 2 (Randomization); and all subsequent visits.

- Weight and height will be measured at Visit 1A (Screening) and, if applicable, Visit 1B (Re-screening). Weight will also be measured at Visit 2 (Randomization), Visit 9 (Week 24), Visit 12 (Week 48), and ET Visit.
- Spot urine protein-to-creatinine ratio will be measured at Visit 2 (Randomization).
- Serum pregnancy test for all women of childbearing potential will be performed at Visit 1A (Screening) and, if applicable, Visit 1B (Re-screening).

Further, serum samples that will be frozen for future analysis of biomarkers of CKD will be obtained at Visit 2 (Randomization), Visit 9 (Week 24), Visit 12 (Week 48), and the ET visit from only those subjects who provided informed consent specifically for their collection.

## 5. PLANNED ANALYSES

The following analyses are planned for this trial:

- A 24-Week Analysis (to be performed after all Screening and Dose Titration Period data are available for all subjects)
- The Final Analysis (to be performed after Database lock, based on data from the entire study).

There will be two analyses; a 24-Week analysis after all subjects complete the 24-Week Dose Titration Period or have been withdrawn from the study and a Final analysis after all subjects either complete or have been withdrawn from the 48-Week study. Both analyses will be done at the end of the study.

Additionally, a “snapshot” of the data for the 24-Week analysis will be presented for publication. This publication will be based on clean data through Week 24 for key safety and efficacy measurements. This will be referred to as the “24-Week analysis snapshot”.

### 5.1. 24-Week Analysis

The 24-Week analysis will be based on the data for all visits up to and including the Week 24 visit, (i.e. it will cover the Dose Titration Period). Data for screen failure subjects will not be cleaned for this analysis.

Data for this analysis are the data for those subjects who completed the Week 24 visit or had Early Termination from the study prior to Week 24. This will be done at the end of the study.

The 24-Week analysis snapshot will be used for a publication. The subset of data will be cleaned and summarized in an abstract after all subjects have completed the 24-Week Dose Titration Period or have been withdrawn from the study. The following variables will be summarized:

- Efficacy analyses for hemoglobin, transferrin saturation, ferritin, serum phosphorus, and estimated glomerular filtration rate (eGFR) will be analyzed using a MMRM model. Additionally, hemoglobin, intact parathyroid hormone (iPTH), C-Terminal fibroblast growth factor 23, and intact fibroblast growth factor 23 will be analyzed using an ANCOVA model. Analyses will use the modified PP Analysis Set.
- Summary statistics for safety analyses, including demographic, baseline characteristics, adverse events, and hematology, chemistry and miscellaneous laboratory tests will be performed. Analyses will use the Safety Analysis Set and modified PP Analysis Set (demographics and baseline characteristics only).

## 5.2. Final Analysis

The final analysis will be based on the full set of cleaned data for all visits up to and including the Week 48 visit (i.e. it will cover the Dose Titration Period and the Dose Maintenance Period).

Data for this analysis are the data for those subjects who completed the Week 48 visit or had Early Termination from the study prior to Week 48.

Some tables, listings and figures produced for the final analysis will display statistics for both the Dose Titration and the Dose Maintenance treatment periods.

## 5.3. Ad Hoc Analysis

There is no ad hoc analysis planned. If an ad hoc analysis is deemed necessary, the SAP will be updated accordingly.

## 5.4. Chronic Kidney Disease Biomarker Analysis

Analyses for the CKD biomarkers from the frozen samples are not covered in this SAP. The analyses and report will be specified in an addendum to the final analysis report.

## **6. GENERAL CONSIDERATIONS FOR DATA ANALYSES AND HANDLING**

Data management will transfer the raw data that were recorded in the eCRF and those data sets from external vendors that contain data to be used in the analyses to Biostatistics for creating the Study Data Tabulation Model (SDTM) and Analysis Data Model (ADaM) datasets. These derived datasets will be created using (SAS®) software. All data analyses will be conducted and summary tables generated using SAS version 9.4 or above.

### **6.1. Data Collection, Processing and Reporting**

Keryx will provide the study sites with secure access to, and training on, the Electronic Data Capture (EDC) application sufficient to permit study site personnel to enter or correct information in the eCRFs on the subjects for which they are responsible. Creation and validation of the clinical database, entry and management of data, and transfer of central laboratory data will be maintained by the Contract Research Organization (CRO) and conducted in accordance with 21 CFR Part 11 [1] and the Guidance for Industry on Computerized Systems Used in Clinical Investigations [2]. 1. U.S. Department of Health and Human Services, Food and Drug Administration. 21 CFR Part 11.2. U.S. Department of Health and Human Services, Food and Drug Administration. Computerized Systems Used in Clinical Investigations, May 2007.

An eCRF will be completed for each enrolled study subject. Data processed at the central laboratory will be transferred electronically. It is the Investigator's responsibility to ensure the accuracy, completeness, clarity and timeliness of the data reported in the subject's eCRF. Source documentation supporting the eCRF data will indicate the subject's participation in the study and will document the dates and details of study procedures, AEs, other observations and subject status. The Investigator or designated representative, will complete the eCRF as soon as possible after information is collected.

Where corrections to an eCRF are needed after the eCRF has been submitted to EDC, the Investigator or appropriate staff member will have to respond with the correct answer. The audit trail entry will show the user's identification information and the date and time of any correction. Details of the data correction (query) process will be specified in the Data Management Plan.

The Investigator will provide formal approval of all the information in the eCRFs, including any changes made to the eCRFs, to endorse the final submitted data for the subjects for whom the Investigator is responsible. CRFs will be completed for all subjects enrolled to study.

## 6.2. Data Presentation Conventions

Unless otherwise stated, all analyses will be performed using SAS® Version 9.4 or higher.

The following formats apply to all tables, figures and listings:

1. p-values will be presented with 3 decimals; p-values that are less than 0.001 will be presented as <0.001. If the rounded result is a value of 1.000, it will be displayed as >0.999. All date information in listings will be presented using 9 character alphanumeric formats (e.g., 01JAN2008).
2. Continuous data will be summarized using descriptive statistics: number of observations (n), mean, standard deviation (SD), median, 25th and 75th percentiles, minimum, and maximum. Given that the 25th and 75th percentiles are the 1st and 3rd quartiles, respectively, they will be labelled as Q1 and Q3, respectively.
3. Unless otherwise specified, in summary tables of continuous variables, the minimum and maximum values will be displayed to the same number of decimal places as the raw data, the mean and median will be presented to one extra decimal place compared to the raw data, and the standard deviation and coefficient of variation will be displayed to two extra decimal places compared to the raw data.
4. Frequencies and percentages will be used to summarize categorical (discrete) data. If there are missing values, the number missing will be presented.
5. Percentages will be based on the non-missing values. Presentations of categorical data will generally suppress percentages for items where the count is zero in order to draw attention to the nonzero counts.
6. Unless otherwise stated, confidence intervals, when presented, will be constructed at the two-sided 95% level.
7. For binomial variables, the confidence intervals will be constructed using the normal approximation without continuity correction due to the relatively large sample size.
8. Wherever possible, data will be decimal aligned.
9. Some laboratory values may be reported as <x, <=x, >x, or >=x due to the limits of detection for a specific assay, where x is the lower or upper limit of detection. For analysis purposes, these values will be treated as x, and for the listings they will be transcribed as from the raw data. (e.g., <x, <=x, >x, or >=x).
10. The listings that display Study Day will have its numeric value, with 'Day' appended as a prefix and a suffix (if applicable) that is:
  - F, if Study Day is the subject's first study medication dose date,

- L, if Study Day is the subject's last study medication dose date and
- P, if Study Day is after the subject's last study medication dose date.

The derivation of study day is outlined in section 6.5.2.

11. In the listings, any subject who is a 'protocol permitted ESA rescue therapy user' will be identified with an asterisk.

### **6.3. Analysis Sets**

Keryx's agreement and authorization of subjects included/excluded from each analysis set will be obtained prior to the 24-Week Analysis snapshot and the Final Analysis database lock.

#### **6.3.1. Screened Subjects**

A screened subject is a person who signs an informed consent form, attends a Screening visit and is assigned a screening ID in IWRS.

#### **6.3.2. Screen Failures**

Subjects who do not meet all the inclusion and exclusion criteria will be considered screen failures. Depending on the reason for screen failure, subjects may be re-screened for study entry at least 2 weeks after their original screen failure date. A subject can be rescreened only once and informed consent must be obtained no more than 7 days before the rescreening. Re-screening will include re-evaluation of all inclusion and exclusion criteria. During screening and/or re-screening (if applicable), subjects may be re-tested for specific inclusion and exclusion criteria that were not met at the initial testing. If a re-test is conducted, it needs to occur within 10 days of Screening (Visit 1A) or Re-screening (Visit 1B).

#### **6.3.3. Safety Analysis Set**

All subjects who take at least 1 dose of study medication will be included in the Safety Analysis Set. The Safety Analysis Set will be used in the assessment and reporting of safety data.

The only study medication to be used is KRX-502. Therefore, treatment groups for the safety analyses will be based on the starting dose of KRX-502 to which subjects were randomized, irrespective of the dose used during the study.

#### **6.3.4. Full Analysis Set**

All subjects who are randomized, take at least 1 dose of study medication and have at least 1 post-randomization efficacy measurement and have the corresponding baseline data will be included in the Full Analysis Set (FAS).

### 6.3.5. Per Protocol Analysis Set

The Per Protocol (PP) Analysis Set will include all subjects in the FAS who have no major protocol deviations that affect the validity of the efficacy measurements (see section 7.2) and have not received additional treatment that affect the validity of the efficacy measurements.

The following criteria exclude a subject from the PP Analysis Set:

- Receive red blood cell transfusions within 4 weeks prior to screening or at any time during the study.
- Receive ESAs (permitted or non-permitted) within 4 weeks prior to screening or at any time during the study.
- Receive IV Iron within 4 weeks prior to screening or at any time during the study.
- Pregnancy during screening or at any time during the study.
- Overall drug compliance < 50% i.e., from randomization to the Week 48 Visit date or to Early Termination date (whichever is earlier). (See section 7.4.1 Compliance Calculation)
- Major violations of eligibility criteria as determined by review prior to database lock.

The PP analysis set will be used for the 24-Week and Final analyses.

### 6.3.6. Modified Per Protocol Analysis Set

The modified Per Protocol (mPP) Analysis Set will include all subjects in the FAS who have no important, i.e., major protocol deviations that affect the validity of the efficacy measurements (see section 7.2).

The following criteria exclude a subject from the mPP Analysis Set:

- Receive red blood cell transfusions within 4 weeks prior to screening or at any time during the study.
- Receive ESAs (permitted or non-permitted) within 4 weeks prior to screening or at any time during the study.
- Receive IV Iron within 4 weeks prior to screening or at any time during the study.
- Pregnancy during screening or at any time during the study.
- Major violations of eligibility criteria as determined by review prior to the snapshot.

The mPP analysis set will be used for the 24-Week analysis snapshot only. The only difference between the PP and mPP is the mPP analysis set is not considering compliance as a criterion for exclusion.

## 6.4. Baseline Definition

The baseline value for each variable, except age, for the 24-Week analysis and the final analysis is the last non-missing value observed prior to administration of the first dose of study medication, irrespective of whether it was a scheduled visit, or unscheduled visit or retest observation.

Unless otherwise indicated, measurements taken on the same day as the first dose are considered to have been taken prior to the first dose.

Each subject's first dose of study medication is prescribed to be consumed on the next day after the Date of Randomization. Because the actual date that the subject takes the first dose may differ from what was prescribed the actual start date will be recorded in the eCRF.

First Dose Date = Study Medication Actual Start Date recorded in the eCRF.

## 6.5. Derived and Transformed Data

### 6.5.1. Baseline Age

Baseline Age (years) will be calculated as

the integer part of  $[(\text{date of informed consent} - \text{date of birth} + 1) / 365.25]$ .

CKD Initial Diagnosis Age (years) will be calculated as

the integer part of  $[(\text{CKD initial diagnosis date} - \text{date of birth} + 1) / 365.25]$ ,

where the CKD initial diagnosis date is imputed using the rule in section 6.6.4, if it contains any missing parts.

### 6.5.2. Study Day

If the date of interest occurs on or after randomization date and on or before treatment end date, then study day will be calculated as

$(\text{date of interest} - \text{date of randomization}) + 1$ .

If the date of interest occurs prior to randomization date, then study day will be calculated as

$(\text{date of interest} - \text{date of randomization})$ .

If the date of interest occurs after treatment end date, then study day will be calculated as

$(\text{date of interest} - \text{treatment end date}) + 1$ .

In this study, there is no Study Day 0 and Study Day 1 is the subject's Randomization Day.

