8.3. Subject Withdrawal Criteria

8.3.1. Discontinuation From Study Drug

Discontinuation from study drug is defined as a permanent termination of treatment with KRX-0502. Subjects may be discontinued from the study drug at any time for any of the following reasons:

- Adverse event
- Lack of efficacy (see [Section 9.2.2](#))
- Pregnancy
- Withdrawal by subject
- Other

If at any time during the course of the study, in the opinion of the Investigator, the subject may no longer safely participate due to a change in medical status (eg, experiences an AE, becomes pregnant), the subject must be discontinued from the study drug.

Whenever study drug is discontinued prematurely, Keryx and the Medical Monitor must be notified. The subject should return for the ET visit and exit the study.

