10.6.2. Procedures for Visit 12 (Week 48) and ET Visit

- Record weight
- Record vital signs
- Review laboratory results from previous visit
- Record AEs
- Record hospitalizations and duration
- Review whether any non-permitted medications were administered since the last visit (see [Section 9.2.1](#) and [Section 9.2.2](#))
- Record changes in concomitant medication and non-drug therapies
- Obtain blood samples:
 - CBC
 - CCP
 - Iron studies
 - iPTH
 - FGF23 (intact and C-terminal)
 - Serum sample for freezing
- Record study drug dosing, review diary, and assess study drug compliance
- Collect study drug and diary
- Administer WPAI questionnaire
- Administer FACIT Fatigue Scale

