**Table 2: Visit Windows (Study Days)**

Visit Number: Visit Name	Analysis Visit Name	Relative Target Day (Study Day)	Visit Window (Study Day Interval)
Visit 1A: Screening a	Screening	-14	<1
Visit 1A: Retest a	Screening	-9 a	<1
Visit 1B: Rescreen b	Screening	-14 b	<1
Visit 1B: Retest b	Screening	-9 b	<1
Visit 2: Randomization	Baseline	1	1
Visit 3: Week 2	Week 2	15	[2, 22]
Visit 4: Week 4	Week 4	29	[23, 43]
Visit 5: Week 8	Week 8	57	[44, 71]
Visit 6: Week 12	Week 12	85	[72, 99]

Document: \\quintiles.net\enterprise\apps\sasdata\sasb\sas\Keryx\KRX-0502\Biostatistics\Documentation\SAP\

Visit Number: Visit Name	Analysis Visit Name	Relative Target Day (Study Day)	Visit Window (Study Day Interval)
Visit 7: Week 16	Week 16	113	[100, 127]
Visit 8: Week 20	Week 20	141	[128, 155]
Visit 9: Week 24	Week 24	169	[156, 197]
Visit 10: Week 32	Week 32	225	[198, 253]
Visit 11: Week 40	Week 40	281	[254, 309]
Visit 12: Week 48	Week 48	337	>309
Visit Early Termination: Early Termination (ET) c	Early Termination		

a Any retest for specific inclusion and exclusion criteria that were not met at the initial testing may occur within 10 days of the original screening date. Therefore, the visit window, including start and end dates, for the retest is the same visit window as that for the original screening visit. A subject can have only 1 retest based on the original screening results.

b Visit window for the rescreen visit has a study day interval relative to Day 1, equivalent to that for the original screening visit but because rescreening of a subject must be at least 14 days after the subject's original screen failure date the actual start and end dates on a subject's Screening Visit window and the Re-Screening Visit window differ. A subject can have only 1 retest based on the re-screening results. Any retest for specific inclusion and exclusion criteria that were not met at re-screening may occur within 10 days of the re-screening date.

c Early Termination visits may fall within a visit window corresponding to a planned study visit. If this is the case, the ET visit will be labeled and summarized with the analysis visit name corresponding to the visit window.

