Multiple assessments may occur within the same window for a variety of reasons, for example, assessments to determine if the study drug dose should be adjusted. While there is only one planned scheduled dose adjustment, unscheduled dose adjustments for a subject may be necessary at any time during the study.

The protocol includes guidance on making dosing adjustments which are dependent on specific central laboratory results. Laboratory values will be checked at each scheduled visit and the study drug dose may be adjusted in response to these results. When laboratory retesting is necessary, it will be done as an unscheduled visit, unless it coincides with a scheduled visit.

Given the time lag in obtaining lab results and communicating the desired dose adjustment to the subject via telephone the time that the new prescription is to start and the subsequent follow-up blood draws for testing may or may not be in a single window for an originally planned visit given in the protocol's schedule of assessments. There may be multiple assessments falling in the same window and multiple assessments related to a single event may be taken during the window for more than one scheduled visit.

Additionally, when a subject discontinues from the study, the assessments made at the Early Termination visit may fall within a window for one of the originally planned visits given in the protocol's schedule of assessments.

When multiple assessments occur within the same window, the one whose date of assessment is the largest study day in the window will be considered as the observed assessment value for that scheduled visit study day.

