## 9. SAFETY AND TOLERABILITY

Safety and tolerability evaluation will be included in the 24-Week Analysis and the Final Analysis.

The safety data includes adverse events, vital signs and clinical laboratory measurements.

Adverse events that begin after the first administration of study medication or pre-existing conditions that worsen after the first dose of study medication are considered TEAEs. If, based upon the data recorded in the eCRF and/or the procedure for imputing the start date given in section 9.2.2, it is not possible to classify an AE as treatment emergent or not, then classify the AE as a TEAE.

For the 24-Week Analysis, since any table, listing or figure produced will only include statistics based upon the Screening period and Dose Titration treatment period:

- No adverse event that starts or worsens after the Week 24 visit date will be included in summaries of TEAEs and
- In calculating the subject months of study drug exposure only those days of treatment prior to the Week 24 visit will be counted since subjects are to delay taking their study drug on the day of planned site visits until after the site visit.

For the Final Analysis, all observations up to and including those for the Week 48 visit date will be included in identifying TEAEs and calculating subject months of study drug exposure.

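### SAP 6.5.2 restarts Study Day after an undefined treatment end date, while the visit windows count from randomization, so Week 48 and Early Termination samples taken after the last dose can go to the wrong analysis visit

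*SAP*

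**What the plan says.** SAP 6.5.2 defines one variable, Study Day, by three rules. Dates before randomization are counted back from randomization. The on-treatment rule begins "If the date of interest occurs on or after randomization date and on or before treatment end date, then study day will be calculated as" and gives the date minus the randomization date, plus one. The third rule begins "If the date of interest occurs after treatment end date, then study day will be calculated as" and gives the date minus the treatment end date, plus one. The section then fixes Study Day 1 as the day of randomization. The term treatment end date appears only here and is not defined.

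SAP 6.5.4, Table 2, expresses its targets and windows in Study Days. Footnote c deals with an Early Termination (ET) visit that falls inside a planned window: "If this is the case, the ET visit will be labeled and summarized with the analysis visit name corresponding to the visit window". When several assessments share a window, "the one whose date of assessment is the largest study day in the window will be considered as the observed assessment value". Nothing in 6.5.4 exempts windowing from the third rule, and no other windowing variable is defined.

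SAP 6.2 adds letter suffixes to Study Day in listings. One of them, P, marks days after the last dose. The same item says: "The derivation of study day is outlined in section 6.5.2".

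**The concern.** The two sections do not fit together. After treatment end the count starts again at 2, the same number as the day after randomization, but Table 2 reads that number as time since randomization.

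Whether this matters depends on what treatment end date means. There are two readings:

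- **(a) It is recorded as the Week 48 or ET visit date.** The final visit is then on treatment and is placed correctly.
- **(b) It is the last dose date.** The restart would then apply routinely. On visit days, according to SAP 9, "subjects are to delay taking their study drug on the day of planned site visits until after the site visit". At Visit 12 and at ET, Protocol 10.6.2 tells sites to "Collect study drug and diary" and provides for no dispensing. For a subject who stops drug early, Protocol 8.3.1 says: "The subject should return for the ET visit and exit the study". Final samples would therefore normally be dated at least one day after the last dose.

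Under (b), Week 48 values leave the Week 48 window and ET values are analysed at an early visit or discarded, which defeats the purpose of footnote c. Visits on treatment are unaffected.

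**Working it through.** **Inputs.** The Study Day rules are from SAP 6.5.2. The windows are from SAP Table 2: Week 2 [2, 22], Week 4 [23, 43], Week 8 [44, 71], Week 12 [72, 99], Week 24 [156, 197], Week 48 above 309. The gap from last dose to sample is not given in the documents, so it is treated as a range.

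**1. Reproduce the plan's targets.** 7 x week + 1 gives 15 for Week 2, 169 for Week 24 and 7 x 48 + 1 = 337 for Week 48. All ten post-baseline targets match and each lies in its own window. The windows are contiguous from Day 1. Table 2 therefore counts from randomization.

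**2. Apply the third rule under reading (b).** With gap g = sample date - last dose date and g of at least 1, Study Day = g + 1, whatever the true day.

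| Gap g (days) | Study Day | Analysis visit |
|---|---|---|
| 0 (second rule applies) | true day | correct |
| 1 to 21 | 2 to 22 | Week 2 |
| 22 to 42 | 23 to 43 | Week 4 |
| 43 to 70 | 44 to 71 | Week 8 |
| 71 to 98 | 72 to 99 | Week 12 |

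- Week 48 visit on true Day 337, last dose on Day 336: 337 - 336 + 1 = 2, so Week 2. Every visit on Days 330 to 344 with a gap of 1 also maps to Week 2.
- To stay in Week 48, g + 1 must exceed 309, so g must be at least 309.
- For an ET sample with true day in the Week 24 window to stay there, g + 1 must be at least 156, so g must be at least 155. Over true Days 156 to 197 and gaps of 1 to 42 (42 x 42 = 1764 combinations), none stays in Week 24.
- At gaps up to 21 days, only ET samples on true Day 22 or earlier keep the right window.

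**3. Apply the rule for several assessments in one window.** A displaced sample has Study Day g + 1 and competes with the real Week 2 sample. If that was taken on Day 15, the displaced one wins only if g + 1 exceeds 15, so for gaps of 15 to 21 days. The range is 12 to 21 if Week 2 was on Day 12, and 18 to 21 if on Day 18. At shorter gaps the displaced sample is discarded. If the rule is read as the latest calendar date, the displaced sample replaces the Week 2 value at every gap from 1 to 21 days.

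**4. Illustrate lost precision at Week 48.** SAP 4.3.1 states a half-width of 0.149 g/dL for the Week 24 hemoglobin (Hgb) change with 140 subjects and SD 0.9. This is reproduced: 1.96 x 0.9 / sqrt(140) = 0.149. Assuming the same SD and number at Week 48, and a simple mean:

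| Week 48 values lost (assumed) | n | 95% CI half-width (g/dL) |
|---|---|---|
| 0% | 140 | 0.149 |
| 25% | 105 | 0.172 |
| 50% | 70 | 0.211 |
| 75% | 35 | 0.298 |

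**The case against.** The harm depends on reading (b), which the documents do not establish. Where the SAP means last dose it says so, in 6.2 and 9.3.1, and 6.5.2 uses a different term. For the Final Analysis, SAP 9 includes observations through the Week 48 visit date when calculating exposure, which fits reading (a). Against that, the exposure formulas in 9.3.1 end at last dose, and the listing rule that cites 6.5.2 is itself built on the last dose date. Neither reading can be excluded, so the finding remains conditional.

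Table 2 also pairs Visit 12 with Week 48 by name. SAP 8.3 allows for visits that are out of window, which hints that scheduled visits keep their identity. This weakens the Week 48 point somewhat. However, 8.3 builds its box plots from observations in the 6.5.4 windows, no sentence exempts Visit 12, and footnote c places ET visits by window in so many words.

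The restart was probably meant for listings. A nearly empty Week 48 column would be easy to notice, and version 1.1 followed a dry run of the outputs. Both points are fair, but the text does not limit the restart to listings, and the analysis should not rely on someone noticing.

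The precision figures are illustrative, and this objection stands. The loss percentages have no source in the documents, routine application would push the loss towards 100%, and the planned Week 48 Hgb analysis is a mixed model for repeated measures (MMRM) with a completer ANCOVA, not a simple mean.

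**Conclusion.** The concern holds as a conditional finding and should be fixed; confidence is medium because the meaning of treatment end date is open. Coded literally with treatment end taken as last dose, SAP 6.5.2 sends every final sample taken 1 to 21 days after the last dose to Week 2. With treatment end taken as the final visit date, or with the last dose on the sample day, that visit is placed correctly.

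The Week 48 endpoints analysed through the windows (Hgb, transferrin saturation, ferritin and phosphate among them) are the most exposed. The Week 24 primary endpoint is touched only through ET visits: samples that belong in the Week 24 window are moved out, and displaced values may enter the early visits of the MMRM. Laboratory shift tables are affected only through post-treatment samples. The number of subjects affected cannot be derived from the documents.

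**What to change.** - In SAP 6.5.2, define Study Day for every date on or after randomization as the date minus the randomization date, plus one.
- In SAP 6.5.4, state that Table 2 windows use only this variable, for scheduled, unscheduled and ET visits alike.
- Define treatment end date as either the last dose date or the visit date, and hold days since last dose in a separate variable used only in listings for the P suffix.

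A Week 48 sample on Day 337 then maps to Week 48 at any gap, and an ET sample on Day 169 maps to Week 24. The change is harmless if reading (a) was intended. It costs two or three sentences in the SAP and a check of the dataset specification, with no new data and no effect on patients.
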